- b. The number and frequency of nCLE procedure-related AE/SAE from the start of the procedure until end of 12-month follow-up
- 8. To assess the reproducibility of nCLE criteria to the reference standard. Three nCLE characteristics for the detection of malignancy were identified during Wijmans et al. study [10]:
 - a. Dark enlarged pleomorphic cells;
 - b. Dark cell clusters consist of overlapping cell structures ('dark clumps') and
 - c. Continuous movement of the cells in one direction ('directional streaming').
- 9. To create an nCLE image atlas for malignant characteristics in PPNs.

3. Study Design

This is a randomized, controlled, interventional, comparative prospective multi-center study. In total, a maximum of 118 consecutive patients with a (suspected) PPN who are referred for a diagnostic bronchoscopic (Robotic-guided TBNA) procedure will be considered for enrollment. The estimated duration of the study is 24 months. Patients will be consecutively recruited and randomly assigned to undergo Robotic-guided TBNA (n=59) or Robotic-nCLE-guided TBNA (n=59).

Only patients in the nCLE arm will receive intravenously administered fluorescein before the start of the Robotic procedure. During the nCLE procedure, an 18G needle enters the targeted tissue, followed by an nCLE AQ-Flex™ 19N Confocal Miniprobe™ (Mauna Kea Technologies, France) through the biopsy needle, to obtain real-time imaging. nCLE imaging will be performed in the PPNs with a total estimated time for research measurements of 10 minutes. nCLE imaging will be performed for each sequential TBNA pass/sampling within the lung nodule lesion and each TBNA path cytopathological result will be correlated with the nCLE sequence acquired for that TBNA pass. TBNA sampling will end when sufficient diagnostic material will be found with ROSE (as assessed by the cytopathologist) or when the physician performing the procedure judges that the number of samplings/passes is adequate. ROSE will be performed by a cytopathologist.

4. Study Population

Population (base)

Patients with a PPN referred for diagnostic bronchoscopic/endosonographic workup tissue sampling based on standard (PET-) CT imaging

Inclusion criteria

To be eligible to participate in this study, a study subject must meet all of the following criteria:

- ≥ 21 years of age
- Suspected PPN
- Nodule size in CT between 8 mm and 30 mm (largest dimension)

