- Ability to understand and willingness to sign a written informed consent and HIPAA consent document

Exclusion criteria

- Inability or non-willingness to provide informed consent
- Failure to comply with the study protocol
- Patients with known allergy for fluorescein or risk factors for an allergic reaction
- Use of beta-blocker within 24 hours before the start of the bronchoscopic procedure
- Possibly pregnant, pregnant or breastfeeding women
- Patients with hemodynamic instability
- Patients with refractory hypoxemia
- Patients with a therapeutic anticoagulant that cannot be held for an appropriate interval before the procedure
- Patients who are unable to tolerate general anesthesia according to the anesthesiologist
- Patient undergoing chemotherapy

Intra-operative Exclusion/Stopping Criteria:

- The lesions are unable to be localized/confirmed by bronchoscopy
- The procedure will be terminated if the patient develops a significant procedural complication as determined by the treating physician
- The procedure will be terminated if the patient develops hemodynamic instability as determined by the treating physician

Sample size calculation

A bronchoscopic TBNA (Robotic-guided TBNA or Robotic-nCLE-guided TBNA) will be regarded as successful when histological confirmation of the diagnosis is achieved and matches the final diagnosis. If additional TBNA passes or tests, e.g., further bronchoscopies, surgery, etc., are needed to establish the diagnosis, the TBNA pass will be regarded as non-diagnostic.

We will calculate TBNA diagnostic yield for the cumulative number of passes until five cumulated passes for both the Robotic-guided TBNA and Robotic-nCLE-guided TBNA arms. It is anticipated that sequential passes at a target site will result in stepwise yield increments to a plateau. Every needle pass at a location will be reported separately and entered into a database to provide yields after each sequential pass.

Proportional data will be compared using a Chi-squared test of contingency tables or Fisher's exact test on 2x2 contingency tables in the case of very small counts (<5).

First- and cumulative-pass diagnostic yields:

Diagnostic yields for the different cumulative passes are defined as follows:

1. First-pass diagnostic yield is calculated as the proportion of patients for which first-pass TBNA during the bronchoscopic procedure yielded a definitive diagnosis out of the total number of patients that have received a diagnostic procedure.

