2. First-two-passes cumulative diagnostic yield is calculated as the proportion of patients for which first-two-passes cumulative TBNA pass during the bronchoscopic procedure yielded a definitive diagnosis out of the total number of patients that have received a diagnostic procedure.
3. First-three-passes cumulative diagnostic yield is calculated as the proportion of patients for which first-three-passes cumulative TBNA pass during the bronchoscopic procedure yielded a definitive diagnosis out of the total number of patients that have received a diagnostic procedure.
4. Etc.... until the fifth pass.

The number of patients has been calculated to demonstrate an increase of the TBNA first-pass diagnostic yield by 20%, from 70% to 90%, between the Robotic-guided TBNA and the Robotic-nCLE-guided TBNA, with a statistical power of 80% with a 2-sided significance level of 0.05. A group size of 59 patients per arm has been derived. By including 59 patients in each arm, we expect to image at least 29 malignant nodules (prevalence of 0.5) in each arm.

The study will enroll 118 consecutive patients randomly assigned 1:1 to Robotic-guided TBNA arm or Robotic-nCLE-guided TBNA arm.

5. Treatment of Subjects

Investigational product/treatment

In recent years, confocal laser endomicroscopy (CLE) has emerged as a novel technique that enables *in vivo* microscopic analysis during ongoing endoscopy [24]. CLE is based on tissue illumination with a low-power laser with subsequent detection of the fluorescence light reflected from the tissue. It is a contrast-based technique, the most widely used agent being the intravenously administered fluorescein. The probe of the endomicroscopy system consists of a flexible catheter probe representing a bundle of optical fibers linked to a micro-objective, a laser scanning unit, and the control and acquisition software (Cellvizio® I.V.E system, Mauna Kea Technologies, France). The principle of the technique is based on a laser beam of the defined wavelength being focused towards the targeted tissue, and the recaptured signal is displayed as 'optical biopsies' in a single horizontal plane.

[figure not shown]

Figure 1: A- Locking of the CLE probe to the aspiration needle. B- CLE probe inside endosonography needle. C- Endosonography images of n-CLE measurements (white arrow) inside a lymph node (LN) (Wijmans/Annema et al. [10]).

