- Accuracy: Probability that a Robotic-guided biopsy gives correct prediction among the total number of cases examined: $= (a + d)/(a + b + c + d)$

Patient diagnostic and management analysis:

Intermediate and final diagnosis and management recommendation proportion differences for the two patient populations (Robotic-guided TBNA arm and Robotic-nCLE-guided TBNA arm) will be compared using a chi-square test. Intermediate and final diagnosis and management recommendation proportions will also be compared for the two patient populations. Differences between Robotic-guided TBNA and Robotic-nCLE-guided TBNA arms regarding the specific diagnostic and management categories will be compared using McNemar's test both at the intermediate diagnosis and the final diagnosis stage.

Feasibility statistical analysis:

The feasibility of needle-based lung cancer diagnosis will be assessed by investigating the following items:

- Assessing nCLE-image quality
- Assessing the feasibility of the integrated needle/Cellvizio® I.V.E Confocal Miniprobe™.

The imaging feasibility yield for the Robotic-nCLE-guided TBNA procedure is defined as the proportion of patients in whom procedure will yield at least good nCLE image quality out of the total number of patients that will receive that procedure.

The mechanical feasibility yield for the Robotic-nCLE-guided TBNA procedure is defined as the proportion of patients for whom Robotic-nCLE-guided TBNA procedure will be possible mechanically (meaning that the nCLE probe will be guided to the nodule successfully) out of the total number of patients that will receive that procedure.

Safety:

The safety will be assessed by carefully monitoring adverse events related to both procedures. Serious adverse event rates will be calculated by dividing the number of events for each procedure divided by the total number of procedures for each arm.

Reproducibility:

To assess the reproducibility of bronchoscopy guided nCLE:

- Estimating the reproducibility of nCLE criteria will be evaluated by calculating the inter-observer agreement of nCLE criteria between 3 readers (Fleiss Kappa).

In Wijmans et al. [10], three nCLE characteristics for the detection of malignancy were identified in different subtypes of lung tumors and metastatic lymph nodes:

- 1) dark enlarged pleomorphic cells;
- 2) dark cell clusters consisting of overlapping cell structures ('dark clumps'); and

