Per patient diagnostic yield of each bronchoscopic procedure (Robotic-guided TBNA and Robotic-nCLE-guided TBNA) will be calculated, and the accuracy of each technique using the final/definitive diagnosis as the reference. The diagnostic yield and accuracy for each method will be compared.

Patient management:

Three therapeutic management options will be considered right after the Robotic-guided TBNA or Robotic-nCLE-guided TBNA: 'neither treatment nor follow-up', 'follow-up', or 'treatment' (see section 6). If the diagnosis is certain, 'neither surgery nor surveillance' will be recommended for benign nodules; treatment will be recommended for malignant lesions; either treatment or follow-up will be recommended for indeterminate nodules.

Overall diagnostic and therapeutic management proportion differences in the two patient populations (Robotic-guided TBNA arm and Robotic-nCLE-guided TBNA arm) will be compared using a chi-square test. Differences between Robotic-guided TBNA and Robotic-nCLE-guided TBNA arms regarding the specific diagnostic and therapeutic management categories will be compared using McNemar's test.

Safety:

One of the secondary goals of the study is to evaluate the safety of Robotic-nCLE-guided TBNA in comparison to Robotic-guided TBNA. According to the validated Common Terminology Criteria for Adverse Events scale (CTCAE: https://ctep.cancer.gov/protocolDevelopment/electronic_applications/docs/CTCAE_v5.0.xlsx). The primary serious adverse event of concern is treatment-induced pneumothorax. Based on data from a recent sizeable multicentric study [27], Robotic-related Common Terminology Criteria for Adverse Events grade 2 or higher pneumothoraces (requiring admission or chest tube placement) occurred in 2.9%. The Robotic-related Common Terminology Criteria for Adverse Events grade 2 or higher bronchopulmonary hemorrhage and grade 4 or higher respiratory failure rates were 1.5% and 0.7%, respectively. Based on these results, we assume that the pneumothoraces rate among similar patients undergoing Robotic-nCLE-guided TBNA procedures will be equivalent to that study.

9. Study Benefit/Risk Ratio

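### McNemar's test, which needs paired results, is assigned to category-by-category comparisons between two independent randomised arms; chi-squared or Fisher's exact test is needed

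*Combined protocol and SAP*

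**What the plan says.** All references are to the combined protocol and SAP.

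- **Section 7, Patient diagnostic and management analysis.** "Differences between Robotic-guided TBNA and Robotic-nCLE-guided TBNA arms regarding the specific diagnostic and management categories will be compared using McNemar's test", and this is to be done "both at the intermediate diagnosis and the final diagnosis stage".
- **Section 8, Patient management.** The assignment is repeated: differences between the arms "regarding the specific diagnostic and therapeutic management categories will be compared using McNemar's test".
- **The same two paragraphs, overall comparison.** Section 7 gives "Intermediate and final diagnosis and management recommendation proportion differences for the two patient populations" to a chi-square test, and section 8 does the same for overall management.
- **Section 4, Sample size calculation.** A generally worded rule: "Proportional data will be compared using a Chi-squared test of contingency tables or Fisher's exact test on 2x2 contingency tables", with Fisher's test kept for counts below 5. On allocation: "The study will enroll 118 consecutive patients randomly assigned 1:1 to Robotic-guided TBNA arm or Robotic-nCLE-guided TBNA arm". Section 3 gives 59 patients per arm. No matching, pairing or crossover is described anywhere.
- **Section 6, Diagnostic and Therapeutic Management.** The tumour board chooses one of three options (treatment, follow-up, or neither) at an intermediate and a final stage. The intermediate diagnosis and recommendation are also to be compared with the final ones. No test is named there.

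**The concern.** McNemar's test compares two proportions measured on the same units. It uses only the pairs whose two results disagree. Here each patient belongs to one arm and has no result under the other, so those pairs cannot be counted. The method cannot be applied as written without an extra step that the plan does not give, and it conflicts with the unpaired test used for the same arms in the same paragraphs.

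At stake are the category-level results: how often each diagnosis and each tumour-board recommendation occurs in each arm, at both stages. Patient management is the subject of the third endpoint in section 8, so these results are likely to be read. If the analyst has to invent a pairing, or quietly replaces the test once data exist, the reported p-values are arbitrary or depart from the plan.

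**Working it through.** **Inputs.** From the documents: 59 per arm, 1:1, two-sided 0.05, first-pass yield 70% v 90%, power 80%, three management options, malignancy prevalence 0.5. All category rates and counts below are assumptions for illustration.

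**1. The plan's own figure treats the arms as independent.** The unpooled formula for two independent proportions gives n = (1.960 + 0.842)² × (0.7×0.3 + 0.9×0.1) / 0.2² = 7.849 × 0.30 / 0.04 = 58.87, rounded up to the stated 59.

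**2. One data set under the unpaired test.** Assume 40/59 v 28/59 in one category.
- Chi-square = 118 × (40×31 − 19×28)² / (68 × 50 × 59 × 59) = 118 × 708² / 11,835,400 = 5.00, p = 0.025.
- Fisher's exact p = 0.040.
- Risk difference = 12/59 = 20.3 points, 95% CI (Newcombe) 2.5 to 36.4.

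Each test gives one value.

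**3. The same data under McNemar with patients paired across arms.** Let a be the number of pairs in which both patients fall in the category. Then b = 40 − a, c = 28 − a, and the statistic is (b − c)²/(b + c) = 144/(68 − 2a). The data fix 40 and 28 but not a, which can be anything from 9 to 28.

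| a | statistic | p |
|---|---|---|
| 9 | 144/50 = 2.88 | 0.090 |
| 15 | 144/38 = 3.79 | 0.052 |
| 19 | 144/30 = 4.80 | 0.028 |
| 22 | 144/24 = 6.00 | 0.014 |
| 28 | 144/12 = 12.0 | 0.0005 |

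Under random pairing a is hypergeometric. The median p is 0.028 and the central 95% runs from 0.014 to 0.052. The two end rows are possible but have probabilities of only about 5×10⁻⁹ (a = 9) and 1×10⁻⁷ (a = 28).

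Over repeated trials, random pairing behaves acceptably. At 59 per arm, exact type I error is 0.052 to 0.054 for equal rates from 0.2 to 0.8 (chi-square 0.049 to 0.053). Power at 0.65 v 0.35 is 0.91, against 0.92 for chi-square. The defect is that the p-value depends on an arbitrary choice. Pairing also leaves patients over if the arms end unequal, which the intra-operative exclusions in section 4 could cause.

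**4. Hypothetical worst case: the arm-by-category table entered directly.** With x/59 and y/59 in the category, the off-diagonal cells are b = 59 − x and c = y. They balance when x + y = 59, so the test asks whether the two rates add to 1, not whether they are equal. Rejection rates with equal arms, by enumerating two independent Bin(59, p):

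| common rate | McNemar, direct entry |
|---|---|
| 0.5 | 0.006 |
| 0.4 or 0.6 | 0.27 |
| 1/3 | 0.81 |
| 0.3 or 0.7 | 0.95 |
| 0.25 | 0.998 |

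- Equal arms, 18/59 v 18/59: b = 41, c = 18, statistic 23²/59 = 8.97, p = 0.003; chi-square p = 1.0.
- Different arms, 39/59 v 20/59: b = 20, c = 20, p = 1.0; chi-square p = 0.0005.
- Power at 0.65 v 0.35: 0.001 or 0.015, depending on column order, against 0.92 for chi-square.

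The last two examples lie where the rates add to 1, which is this misuse's blind spot. Away from it, at 0.5 v 0.2, it rejects 0.55 to 0.86 of the time, though still not as a test of equality. Because the three management options add to 100%, at least one has a rate of 1/3 or less. If treatment followed the assumed malignancy prevalence of 0.5, at least one other option would be at 0.25 or less.

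**The case against.** **Perhaps a within-patient comparison was meant.** Intermediate and final recommendations are two results on the same patient, and a paired test would suit them. Section 7 also has a sentence, between the chi-square and McNemar sentences, saying that intermediate and final proportions will be compared, with no test named. But the McNemar sentence names the arms as the things compared and the stages as the times of comparison, and section 8 repeats it between arms with no mention of stages. This may explain how the error arose; it does not make the text right.

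**Random pairing is not an invalid test.** This stands. Its error rate and power are close to chi-square, so it would be wrong to say that every way of running the test gives false results.

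**Nothing says the table will be entered directly.** This also stands. A reader might infer from the 81% and 99.8% figures that the planned analysis has a grossly inflated error rate. The documents do not support that: the figures describe a possible mistake in carrying out the plan. The loss of power is likewise confined to rates that add to about 1.

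**Little depends on it.** Secondary objectives 2 and 3 concern the proportions of patients with lung cancer treatment and with follow-up procedures, and the section 4 rule covers plain proportions of that kind. The category comparisons of tumour-board diagnoses and recommendations carry no power claim. This limits the weight of the point but does not remove it, because a prespecified method that cannot be applied as written still has to be replaced.

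**Conclusion.** The test is wrong as written in both sections. McNemar's test does not apply to two independent arms, and the plan's own overall chi-square and rule for proportions contradict it. This rests on the text alone and on no assumed rate.

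The certain consequence is moderate: the p-value is not determined by the data. In the assumed example it moves across 0.05 (0.014 to 0.052 in the central 95% of random pairings) where chi-square gives 0.025. The severe consequence, equal arms declared different most of the time, arises only if an analyst feeds the unpaired table to the test and the category rate is well away from one half.

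A reader might also infer that the trial's main conclusion is at risk. It is not: the primary endpoint, the sample size of 59 per arm and the overall management chi-square are untouched. The point should be corrected, but it concerns non-primary analyses only.

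**What to change.** In section 7 (Patient diagnostic and management analysis) and section 8 (Patient management), replace McNemar's test with the section 4 rule. Each diagnostic and management category is then compared between arms by a chi-squared test, or by Fisher's exact test for counts below 5; in section 7 this applies at the intermediate and at the final stage. Preferably, report a risk difference with a 95% confidence interval for each category.

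If the within-patient comparison of intermediate with final diagnosis and recommendation (section 6) is to be tested formally, name a McNemar-type test for that purpose only. If it is descriptive, say so; no paired test is then needed.

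The cost is one sentence in each of two sections. No new data are needed, and neither the primary analysis nor the sample size changes. The edit should be made before outcome data are seen, so that it is not a post hoc change of method.
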